### Criteria for Establishing Efficacy

While several supportive and/or supplementary analyses are specified above, the main criterion for demonstrating efficacy will be the primary analysis using the log transform for the mITT population. It is conceivable that some or all of these supplemental analyses may not reach statistical significance. However, it is expected that the direction of effect will be in favor of the test treatment. As an example, a statistically significantly smaller least squares adjusted MCSF for the treatment group compared to placebo, in the presence of a smaller proportion of subjects on 0.8 mg/kg than Placebo subjects increasing their dose of concomitant AEDs will be strong evidence for efficacy of the experimental treatment.

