### 2.5. Determination of Sample Size

The sample sizes for Zogenix Studies 1501 and 1502 were calculated based on the results of two trials with stiripentol reported in the European Public Assessment Report (EPAR) for stiripentol (EMA, 2007). The stiripentol EPAR summarizes the results from two studies: STICLO France and STICLO Italy. In the stiripentol groups, the standard deviation (SD) of the percentage change in seizure frequency from baseline to month 2 was 42% in the French trial and 26% in the Italian trial. The analogous SDs for placebo groups were 38% and 62%. An SD of 50% was assumed for the primary analysis in Protocols 1501 and 1502 that compares ZX008 0.8 mg/kg/day to placebo on the change from baseline in seizure frequency. Using a two-sided test at the  $\alpha=0.05$  significance level, a sample size of 35 subjects per treatment group affords 90% power to detect a difference in mean change from baseline of 40 percentage points. Similar assumptions and calculations yielded a requirement for an additional 35 subjects in the 0.2 mg/kg/day ZX008 group. The total sample size for each study was therefore set at 105 subjects.

In December 2016 results from a double-blind, placebo-controlled Phase 3 study with Epidiolex® (cannabidiol) to treat seizures in Dravet syndrome were presented at the American Epilepsy Society Meeting (<http://ir.gwpharm.com/events.cfm>). In the Epidiolex study, active drug reduced seizures by 39% compared to a reduction of 13% in the placebo. Review of the data suggested that the standard deviation was relatively large, likely above 50% in both treatment groups. In consideration of this new data, the sample size was re-estimated for the ZX008 studies to assume a SD of 55%, higher than the previous estimate of 50%. Other assumptions in the sample size calculation remained unchanged. A sample size of approximately 120 subjects (40 per arm) affords 90% power to detect a difference in mean change from baseline of 40 percentage points with 55% SD. Considering the variability seen in the STILCO and Epidiolex trials, the sample size for Study 1 and Study 2 is set at 120 subjects, 40 per treatment arm. Note that the change in assumed SD was based entirely on data from external trials. Efficacy data from both Study 1501 and 1502 are still blinded and were not used in re-estimating the required sample size.

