### 2.6. Treatment Assignment & Blinding

Subjects in Study 2 were originally in either Study 1501 or Study 1502. Upon completion of the Baseline Period, subjects who qualify for the study will be randomized (1:1:1) in a double-blind manner to receive 1 of 2 doses of ZX008 (0.2 mg/kg/day, 0.8 mg/kg/day; 30mg/day maximum) or placebo. The randomization was stratified by age (<6 years,  $\geq 6$  years) to ensure balance across treatment arms, with

This document is confidential.

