## Statistical Analysis Plan

Sponsor: Zogenix International Limited; Protocol No.: ZX008 Study 2 (ZX008-1501 and ZX008-1502)

---

The efficacy analyses will employ a serial gatekeeper strategy to maintain the Type 1 error rate at  $\alpha=0.05$  across the family of analyses that support the primary and key secondary objectives.

All statistical analyses will be performed and results tabulated with test statistics, p-values, and/or 95% confidence intervals.

Formal statistical testing will be performed for 1 primary endpoint and 2 secondary endpoints, for the comparison of ZX008 0.8 mg/kg with Placebo, and between ZX008 0.2 mg/kg with Placebo. Hence there are 6 formal hypothesis tests: 1 primary hypothesis test and 5 secondary hypothesis tests. To preserve the overall Type 1 error rate at  $\alpha=0.05$ , these tests will proceed as follows:

Step 1: The primary efficacy endpoint (mean convulsive seizure frequency per 28 days) will be formally tested first between the 0.8 mg/kg and Placebo group. If the comparison is statistically significant at the  $\alpha=0.05$  (2-sided) level, hypothesis testing will proceed to Step 2. Otherwise formal testing of the other hypotheses stops.

Step 2: The secondary efficacy endpoint, the proportion of subjects who achieve a  $\geq 50\%$  reduction from baseline in convulsive seizure frequency, will be compared between the 0.8 mg/kg and Placebo group. If the comparison is statistically significant at the  $\alpha=0.05$  (2-sided) level, hypothesis testing will proceed to Step 3. Otherwise formal testing of the other hypotheses stops.

Step 3: The endpoint, the longest convulsive seizure-free interval will be compared between 0.8 mg/kg and Placebo. If the comparison is statistically significant at the  $\alpha=0.05$  (2-sided) level, hypothesis testing will proceed to Step 4. Otherwise formal testing stops.

Step 4: The mean convulsive seizure frequency per 28 days will be formally tested first between the 0.2 mg/kg and Placebo group. If the comparison is statistically significant at the  $\alpha=0.05$  (2-sided) level, hypothesis testing will proceed to Step 5. Otherwise formal testing of the other hypotheses stops.

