## Primary Analysis

### T+M Period:

The primary analysis will compare the ZX008 0.8 mg/kg/day group to the placebo group using a two-sided test at the  $\alpha=0.05$  level of significance.

The primary endpoint ( $CSF_{T+M}$ ) will be analyzed using an analysis of covariance (ANCOVA) model with treatment group (three levels) and age group (< 6 years,  $\geq 6$  years) as factors, log baseline  $CSF_B$  as a covariate and log  $CSF_{T+M}$  as response. Treatment group mean differences from placebo will be estimated via least squares means from the analysis model along with 95% confidence intervals and associated 2-sided p-values. Estimated treatment differences and CI endpoints will be exponentiated for presentation.

The null hypothesis

$$H_0: \mu_{Z0.8} - \mu_P = 0,$$

will be tested against the alternative

$$H_A: \mu_{Z0.8} - \mu_P \neq 0,$$

where  $\mu_{Z0.8}$  and  $\mu_P$  represent the ZX008 0.8 mg/kg and Placebo group means (on the log scale), respectively.

Rejection of the null hypothesis in favor of the alternative, in the presence of a statistically significantly smaller mean convulsive seizure frequency for the treatment group compared to the placebo group, (two-sided p-value < 0.05) will be regarded as evidence of a treatment benefit in favor of the 0.8 mg/kg group.

Sample SAS code for the ANCOVA described above is as follows:

```
proc glm data=temp;
  class agegrp trtp;
  model csftm = bcsf agegrp trtp / SS3;
  lsmeans trtp / pdiff stderr;
```

where trtp = randomized treatment group (with codes 1, 2, 3 indicating placebo, 0.2 mg, and 0.8 mg groups).

```
bcsf = log( CSFB ),
csftm = log( CSFT+M + 1 ),
agegrp = age group.
```

Additional statements may be used to obtain estimates and associated 95% confidence intervals. Endpoints of the CIs may be exponentiated to obtain CI on the original scale. Fitted values and residuals will be plotted to check model assumptions.

Since the ANCOVA used in the primary analysis relies on assumptions of normality, the primary endpoint will also be analyzed using a nonparametric method that does not require as stringent assumptions. A nonparametric ANCOVA will be used to analyze the data, with ranks of the baseline  $CSF_B$  as a covariate and ranks of  $CSF_{T+M}$  as response, and the results will be used to assess the primary objective. If normality assumptions are not met, the results of the nonparametric test will be used to assess the primary objective.

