## 8.2. Secondary Efficacy Endpoint(s) and Analyses

### 8.2.1. Key Secondary Analysis

#### **MCSF for ZX008 0.2 mg/kg/day versus Placebo**

The MCSF during the T+M period will be analyzed and compared between the ZX008 0.2 mg/kg/day group and the placebo group using the same methods employed for the primary analysis. Following the same strategy as the ZX008 0.8 mg/kg/day comparison, a nonparametric analysis using ranks will be used for the ZX008 0.2 mg/kg/day comparison if the assumptions of the parametric ANCOVA model are not met.

The analysis will be repeated for the M period.

This document is confidential.

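### The SAPs give conflicting rules for which test decides the primary endpoint, and no criterion for switching from the log-scale to the rank ANCOVA

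*SAP*

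**What the plan says.** The same text stands in the Study 1 SAP (6.3.1.1) and the Study 2 SAP (8.1, Primary Analysis). The response is log convulsive seizure frequency over titration plus maintenance, in an ANCOVA with treatment, age group and log baseline. The hypotheses are written for log-scale means. A smaller mean with "two-sided p-value < 0.05) will be regarded as evidence of a treatment benefit in favor of the 0.8 mg/kg group".

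Three statements then bear on which test decides:

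- **Rank ANCOVA, no condition.** Near the end of 6.3.1.1 and 8.1, a rank ANCOVA is added and its results are assigned to the primary objective.
- **Rank ANCOVA only as a fallback.** The next sentence reads: "If normality assumptions are not met, the results of the nonparametric test will be used to assess the primary objective". Section 3.1 of the Study 2 SAP repeats this conditional form.
- **Log ANCOVA.** Under Criteria for Establishing Efficacy (Study 1 SAP 6.3.1.2; Study 2 SAP 8.1), "the main criterion for demonstrating efficacy will be the primary analysis using the log transform for the mITT population". The fallback is not mentioned.

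The only check described is a plot of fitted values and residuals, optional in the Study 1 SAP and planned in the Study 2 SAP. For 0.2 mg/kg/day (Study 1 SAP 6.3.2.1; Study 2 SAP 8.2.1), ranks are used for the "comparison if the assumptions of the parametric ANCOVA model are not met", again without a criterion. On error control, Study 2 SAP 6.3 states: "The efficacy analyses will employ a serial gatekeeper strategy to maintain the Type 1 error rate at" 0.05; Study 1 SAP 6.1.2 says the same.

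**The concern.** Step 1 is the gate for all five later formal tests, and Step 4 depends on the same unresolved choice. Two p-values will be available for each comparison, because the parametric and nonparametric mITT analyses have their own planned tables (14.2.1.2 and 14.2.1.3 in both SAPs). If the residuals look non-normal, the conditional rule sends the decision to ranks, while the criteria section, read on its own, leaves it with the log analysis. If they look borderline, nothing says which side of the line they fall on. Where the two tests differ, success at Step 1 could then turn on a judgement that the plan does not constrain.

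Timing adds to this. The fitted model contains randomized treatment, so its residuals appear to need the treatment codes. The interim analysis sections (Study 1 SAP 6.7; Study 2 SAP 11) say what must be settled before unblinding: data cleaning and the per-protocol exclusions. The choice of primary test is not on that list.

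**Working it through.** **The plan's own figure first.** Study 2 SAP 2.5 says that 40 per arm "affords 90% power to detect a difference in mean change from baseline of 40 percentage points with 55% SD", and that "the sample size for Study 1 and Study 2 is set at 120 subjects, 40 per treatment arm"; allocation is 1:1:1 (2.6). With a two-sided 0.05 test, power = Φ(40 / (55 × √(2/40)) − 1.96) = Φ(3.25 − 1.96) = 90.2%, or 89.5% by the noncentral t. The stated 90% reproduces, and this point does not affect it.

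**The rules side by side, if normality is judged to have failed**

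| Statement | Deciding test |
|---|---|
| Unconditional clause, 6.3.1.1 / 8.1 | Rank |
| Next sentence, and Study 2 SAP 3.1 | Rank |
| Criteria for Establishing Efficacy | Log |

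If normality is judged to hold, the unconditional clause still points to ranks and the other two point to the log analysis. No reading satisfies all three in both cases.

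**Type I error at Step 1.** I took 20,000 null trials per scenario, with three arms of 40. The log test is ANCOVA of log(CSF+1) on log baseline, age group and treatment. The rank test is the same model on ranks; keeping age group in it is an assumption, since the SAPs mention only ranked baseline and ranked response. Assumptions not in the documents:

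- log baseline rate per 28 days normal with mean 3 and SD 1;
- Poisson counts over 42 and 98 days;
- 25% of subjects under 6 years;
- on-treatment log-scale errors normal (SD 0.6), heavy-tailed (t, 3 df), skewed, or normal with 8% of subjects seizure-free.

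Extreme rates were truncated in the last three scenarios. The fixed switch uses ranks when Shapiro–Wilk on the treatment-adjusted residuals gives p < 0.05. Either significant = log + rank − both; disagree = log + rank − 2 × both.

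| Errors | Log alone | Rank alone | Both | Either | Disagree | Shapiro–Wilk rejects | Fixed switch |
|---|---|---|---|---|---|---|---|
| Normal | 4.87% | 5.03% | 3.48% | 6.42% | 2.94% | 5.0% | 4.87% |
| Heavy tails | 5.10% | 5.22% | 3.43% | 6.89% | 3.46% | 77.6% | 5.25% |
| Skewed | 4.89% | 4.71% | 3.43% | 6.17% | 2.74% | 99.9% | 4.72% |
| 8% zeros | 5.01% | 5.02% | 3.63% | 6.40% | 2.77% | 99.9% | 5.03% |

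The Monte Carlo standard error near 5% is √(0.05 × 0.95 / 20,000) = 0.15 points. A separate, smaller simulation with overdispersed daily counts (4,000 and 3,000 null trials, standard error about 0.4 points) gave 7.0% and 5.9% for either test significant.

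**Step 4.** With 0.8 mg/kg/day effective (a shift of −1.0 on the log scale), 0.2 mg/kg/day null and Steps 2 and 3 assumed passed, the error is 5.3% with the log test fixed and 6.9% with free choice, a difference of 1.6 points.

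**What the table shows.** Either test alone holds about 5%. So does a switch under a written rule, even on treatment-adjusted residuals. Only free choice of the smaller p-value raises the error. The rejection rates of 5.0% to 99.9% show that, under even one simple criterion, whether the fallback is used depends heavily on the shape of the data.

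**The case against.** The strongest defence is that the intended rule can be made out. Section 3.1 of the Study 2 SAP, the last sentence of the primary analysis text and the 0.2 mg/kg/day sections agree: log ANCOVA by default, ranks if assumptions fail. The hypotheses are on the log scale. The criteria section opens by contrasting the primary analysis with the supplementary ones, so it may be ranking the primary analysis above those without addressing the fallback. The unconditional clause then looks like a drafting slip that the next sentence corrects. Both results have planned tables, so neither can be hidden.

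Much of this stands: the default order is discernible, and under the conditional rule the assumption check, not the p-value, decides. It does not supply a definition of failed normality, and it does not remove the unconditional clause, which remains in both SAPs.

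A reader might go further and infer that the 5% error rate is broken. The documents do not support that. The stated trigger is failed assumptions, not significance; nothing permits choosing the smaller p-value; and a fixed switch held 4.7% to 5.3%. A reader might also take it as stated that the check is made unblinded. It is not: this is inferred from a model containing treatment and from the absence of any named blinded check.

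**Conclusion.** The point holds as a defect of specification. The SAPs contain incompatible statements of the deciding test, and the switch at Steps 1 and 4 has no criterion, time point or assessor. Strict 5% control of the gatekeeping sequence is not guaranteed, which is weaker than saying it is lost. In the worst case, a choice that follows the smaller p-value, Step 1 error is about 6–7%. That range rests on assumed seizure-count distributions and 40 per arm. The tests disagree on significance in about 3% of null trials, and in those trials the undefined criterion could determine the outcome. Because this is the success criterion at the head of a fixed sequence, and the correction is cheap, it should be corrected.

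**What to change.** Name one deciding test for Steps 1 and 4. The simplest choice, consistent with the criteria section and the log-scale hypotheses, is the log(CSF+1) ANCOVA, with the rank ANCOVA always reported as a sensitivity analysis. Delete the unconditional clause in Study 1 SAP 6.3.1.1 and Study 2 SAP 8.1. Amend the conditional sentence in the same two sections, and the fallback wording in Study 1 SAP 6.3.2.1 and Study 2 SAP 3.1 and 8.2.1. Editing only the primary analysis text would leave a new contradiction with 3.1 and with the 0.2 mg/kg/day sections.

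Alternatively, keep the fallback but write a numerical criterion, apply it to blinded pooled data, document the outcome before unblinding, and refer to it in the criteria section of both SAPs.

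The Study 2 SAP (2.3) describes Study 1 as already reported, so for Study 1 the change would be a documented clarification of which rule applied.

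The cost is wording. Both analyses are already planned; under the first option the sponsor gives up a discretionary fallback.

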## Statistical Analysis Plan

Sponsor: Zogenix International Limited; Protocol No.: ZX008 Study 2 (ZX008-1501 and ZX008-1502)

---

A similar ANCOVA model will be used, and if distributional assumptions are not met, a nonparametric analysis will be performed.

Treatment by baseline seizure category interaction: The primary analysis described above will be repeated with baseline seizure frequency as a categorical variable, rather than a covariate. Baseline seizure frequency per 28 days will be categorized as either < 10; 10-50; or >50.

## Supplementary and Sensitivity Analyses

### Per protocol Analysis

Additionally, the primary efficacy analysis will be repeated on the per protocol population (which excludes subjects with important protocol deviations that may affect the inference on efficacy such as a change in dose or type of concomitant AED medication).

### Percentage Reduction from Baseline

The ANCOVA employed in the primary analysis uses log CSFT+M as the response adjusts for baseline seizure frequency by incorporating CSFB as a factor in the model. The alternative approach described here calculates the percentage change in CSF from baseline directly and uses that quantity as the response variable in an ANCOVA model. Specifically, the ANCOVA will use the percentage change from the T+M period to baseline as the response variable, baseline CSF as a covariate, and treatment and age stratum as classification factors. The analyses will be repeated for the M period only using the baseline as covariate.

If the distributional assumptions for the parametric analysis are not met, a nonparametric ANCOVA will be used for the ranks of the dependent variable as response, using the ranks of the baseline as covariate.

### Criteria for Establishing Efficacy

While several supportive and/or supplementary analyses are specified above, the main criterion for demonstrating efficacy will be the primary analysis using the log transform for the mITT population. It is conceivable that some or all of these supplemental analyses may not reach statistical significance. However, it is expected that the direction of effect will be in favor of the test treatment. As an example, a statistically significantly smaller least squares adjusted MCSF for the treatment group compared to placebo, in the presence of a smaller proportion of subjects on 0.8 mg/kg than Placebo subjects increasing their dose of concomitant AEDs will be strong evidence for efficacy of the experimental treatment.

## 8.2. Secondary Efficacy Endpoint(s) and Analyses

### 8.2.1. Key Secondary Analysis

#### **MCSF for ZX008 0.2 mg/kg/day versus Placebo**

The MCSF during the T+M period will be analyzed and compared between the ZX008 0.2 mg/kg/day group and the placebo group using the same methods employed for the primary analysis. Following the same strategy as the ZX008 0.8 mg/kg/day comparison, a nonparametric analysis using ranks will be used for the ZX008 0.2 mg/kg/day comparison if the assumptions of the parametric ANCOVA model are not met.

The analysis will be repeated for the M period.

This document is confidential.

### Proportion with $\geq 50\%$ Reduction from Baseline in Convulsive Seizure Frequency

Subjects with a percent reduction in convulsive seizures of at least 50 percentage points from baseline will be identified and the overall proportion within each treatment tabulated. That is, the proportion of subjects in the ZX008 0.8 mg/kg/day group who have a decrease in convulsive frequency of at least -50 percentage points will be compared to the analogous proportion in the placebo group.

Similarly, the proportion of subjects in the ZX008 0.2 mg/kg/day group who have a change in convulsive frequency of at least -50 percentage points will be compared to the analogous proportion in the placebo group.

The comparison between treatment groups will be made using a logistic regression model that incorporates the same factors as the ANCOVA used in the primary analysis. This will model a categorical response variable (achieved 50 percentage point reduction, yes or no) as a function of treatment group (ZX008 and placebo) and age group (< 6 years,  $\geq 6$  years). Comparisons between treatment groups will also be made using pairwise Fisher's exact tests since the logistic regression models may not converge in all circumstances.

Raw descriptive statistics will be presented by treatment group, and will include the number and proportion of subjects < 6 years,  $\geq 6$  years, and overall achieving the reduction along with the model estimated odds ratio (including a 95% confidence interval) and p-values from both logistic regression and Fisher's test for comparison of ZX008 0.8mg/kg/day to placebo and ZX008 0.2mg/kg/day to placebo separately.

### Longest Interval between Convulsive Seizures

The longest interval between convulsive seizures will be analyzed.

For each subject, the longest interval between convulsive seizures will be calculated over the entire T+M period. This will be derived as the maximum of the number of days between consecutive convulsive seizures. The intervals between consecutive convulsive seizures will be calculated as below, after which the longest interval between convulsive seizures will be derived.

If a subject has two consecutive days of missing diary data, the current seizure-free interval will be ended on the first date of missing diary data, and a new one begun on the next date that diary data are available and no seizure occurs. [In that case, for purpose of calculation of this variable, all intervening days, after the 2nd day, with missing diary data, will be assumed to have a convulsive seizure occurrence, until the first available date with non missing diary data.]

Let Date0 (=Day1) be the first day of treatment. If convulsive seizure occurs on five days having dates as Date1, Date2, Date3, Date4 and Date5, where Date5>Date4>Date3>Date2>Date1 $\geq$ Date0, and let LDT = Last date of treatment in the maintenance period, where LDT  $\geq$  Date5, then the time interval between convulsive seizures will be calculated as follows:

$$I1 = \text{Date2} - \text{Date1}$$

$$I2 = \text{Date3} - \text{Date2}$$

$$I3 = \text{Date4} - \text{Date3},$$

$$I4 = \text{Date5} - \text{Date4}.$$

For completeness, we calculate the time to the first seizure as

This document is confidential.

